## **9.0 Efficacy Analyses**

### **9.1 General Considerations**

The efficacy endpoints for migraine day, headache day and acute medication use day are defined in protocol Section 8.1. All efficacy analyses will be conducted in the mITT Population in support of submission in the US and in the Off-treatment Hypothetical Estimand population in support of European submissions.

The primary analysis will be performed after all ongoing participants have completed the double-blind treatment period and follow-up period and the database has been locked. This will be the only and final analysis for the secondary efficacy endpoints as well as all other efficacy endpoints in the double-blind treatment period.

Unless otherwise specified, any participant who is randomized based on a wrong stratum will be analyzed according to the actual stratum the participant belong to.

### **9.2 Handling of Missing Data**

Missing data will be handled using the following methods for the primary efficacy analysis. Details can be found in Section [9.3.2](#) and Section [9.3.3](#).

- Mixed model for repeated measures (MMRM) based on observed data collected during the double-blind treatment period (Primary efficacy approach for the US)
- ANCOVA model based on 3-month average of the monthly migraine days
- Within-group imputation based on observed data

- Copy-reference approach
- MMRM based on primary measures collected during the double-blind and follow-up periods (Primary efficacy approach for the EU)

### **9.3 Primary Efficacy Endpoint(s) and Analyses**

#### **9.3.1 Primary Efficacy Endpoint(s)**

The primary efficacy endpoint is the change from baseline in mean monthly migraine days across the 12-week treatment period. Baseline is defined as the number of migraine days during the last 28 days prior to the randomization date.

#### **9.3.2 Main Analysis of Primary Efficacy Endpoint**

The attributes of the estimands corresponding to the primary efficacy endpoint are summarized in [Table 4](#).

**Table 4. Summary of the Estimand Attributes of the Primary Efficacy Endpoint**

Estimand Label	Attributes of the Estimand				
	Treatment	Endpoint	Population	Handling of Intercurrent Events	Statistical Summary
Primary in support of the European submissions	Arm A: Placebo Arm B: Atogepant 60 mg QD Acute migraine medications as rescue medications are allowed to keep participants in the study	Change from baseline in mean monthly migraine days across the 12-week treatment period	The Off-treatment Hypothetical Estimand Population (see Section 4.0)	IE1: Regardless of whether allowed rescue medications are taken or not, data are included in the analysis. IE2: Participants who start a new migraine prophylaxis treatment during the double-blind or safety follow-up period will have their data after starting the new migraine prophylaxis treatment during the follow-up period excluded from the analysis. IE3: Participants who discontinue study treatment due to all reasons other than starting a new migraine prophylaxis treatment will have their data collected after discontinuation of study treatment, and those off-treatment data will be included in the analysis.	The difference in mean change from baseline in mean monthly migraine days across the 12-week treatment period between atogepant group and placebo

Estimand Label	Attributes of the Estimand				
	Treatment	Endpoint	Population	Handling of Intercurrent Events	Statistical Summary
Primary in support of the submission in the US	Arm A: Placebo Arm B: Atogepant 60 mg QD Acute migraine medications as rescue medications are allowed to keep participants in the study	Change from baseline in mean monthly migraine days across the 12-week treatment period	The Modified Intent-to-Treat (mITT) Population (see Section 4.0)	IE1: Regardless of whether allowed rescue medications are taken or not, data are included in the analysis. IE2: Data after the discontinuation from double-blind treatment period are excluded and assumed missing at random.	The difference in mean change from baseline in mean monthly migraine days across the 12-week treatment period between atogepant group and placebo

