- ⁿ EQ-5D-5L will be collected via an eDiary for a period of 1 week in the screening period (administered between the 22nd and 28th days of the Screening/baseline period for a total of 7 days), randomization (Study Day 1) until Visit 3 (14 consecutive days from randomization), Visit 4 (\pm 3 days ie, Study Days 25 to 31 from randomization for a total of 7 days), Visit 5 (\pm 3 days ie, Study Days 39 to 45 from randomization for a total of 7 days), Visit 6 (\pm 3 days ie, Study Days 53 to 59 from randomization for a total of 7 days), and Visit 7 ($-$ 7 days ie, Study Days 77 to 83 from randomization for a total of 7 days). At Visit 8, the EQ-5D-5L will be administered in an eTablet.
- ^o The first dose of study intervention should be taken at the study site
- ^p Collected at Visit 2 only for participants who fail screening
- ^q Collected at Visit 7/ET only for participants who complete the double-blind treatment period
- ^r Collected at Visit 8/EOS only for participants who terminate early from the double-blind treatment period
- ^s For participants who terminate early from the double-blind treatment period only.

2. Introduction

Atogepant is a potent, selective oral calcitonin gene-related peptide receptor antagonist (CGRP-RA) being developed for the prophylaxis of migraine.

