9.6.4. Accounting of Intercurrent Events

Intercurrent events and their handling rules are as follows:

- Participants who start a new migraine prophylaxis treatment during the double-blind or safety follow-up period will have their data during the safety follow-up period after starting the new migraine prophylaxis treatment excluded from the data analysis.
- Participants who discontinue study intervention due to all reasons other than starting a new migraine prophylaxis treatment will have their data collected after discontinuation of study intervention and those off-treatment will be included in the analysis.

Detailed methods and procedures will be documented in the SAP prior to study completion.

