10.8.4. Visit 7/Early Termination (Week 12)

- Effort should be made by the site to not schedule Visit 7 earlier than 12 weeks after Day 1 to ensure participants complete the full 12 weeks of treatment and have eDiary data through Day 83. Prior to any other test or evaluations, administer PRO measures, including: HIT-6, PGIC, PGI-S, WPAI:MIGRAINE, PSSM, MIDAS, MSQ v2.1, PROMIS-PI and PHQ-9.
- Review eDiary data and compliance.
- Complete Healthcare Resource Utilization Questionnaire
- Collect eDiary, only from participants who completed the double-blind treatment period (Visit 2 to Visit 7/ET; for participants who discontinue study, eDiary collection will occur at Visit 8)
- Perform physical examination.
- Perform urine pregnancy test for women of childbearing potential.
- Collect vital sign measurements (weight, pulse rate, respiratory rate, blood pressure, and body temperature).
- Assess C-SSRS on eTablet (the “Since Last Visit” assessment of the C-SSRS will be completed).
- Perform and transmit ECG.
- Update concomitant medications and procedures.
- Review and assess AEs.
- Collect blood and urine samples for chemistry, hematology, INR, and urinalysis.
- Collect post-dose PK sample (for participants who consented). The PK sample should be collected 1 to 10 hours post the daily dose.
- Collect previous visit study intervention, review participant compliance, and perform accountability.
- Access IWRS and enter accountability.
- Advise participants who early terminated from the double-blind treatment period to continue completing their eDiary through the Follow-up Visit. Remind participant to bring eDiary to next visit.

10.8.5. Visit 8 (End of Study) Week 16

- Prior to any other test or evaluations, administer PRO measures, including: EQ-5D-5L, HIT-6, and MSQ v2.1.
- Collect eDiary from participants who early terminated from the double-blind treatment period, review eDiary data and compliance.
- Perform physical examination.
- Assess C-SSRS on eTablet (the “Since Last Visit” assessment of the C-SSRS will be completed).
- Collect vital sign measurements (weight, pulse rate, respiratory rate, blood pressure, and body temperature).
- Perform urine pregnancy test for women of childbearing potential.
- Collect blood and urine samples for chemistry, hematology, INR, and urinalysis.
- Update concomitant medications and procedures.
- Review and assess AEs.
- Access IWRS to enter study visit.

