## 2.1 Objectives, Hypotheses and Estimands

Objectives	Hypotheses	Estimands
Primary Efficacy		

To prospectively test for superiority of atogepant 60 mg QD versus placebo for the prevention of migraine in participants with episodic migraine who have previously failed 2 to 4 classes of oral medications for the prophylaxis of migraine
	
Null: atogepant 60 mg QD is equally effective to placebo in decreasing from baseline in mean monthly migraine days across the 12-week treatment period
 
Alternative: atogepant 60 mg QD is superior to placebo in decreasing from baseline in mean monthly migraine days across the 12-week treatment period
	
Efficacy is to be measured using change from baseline in mean monthly migraine days across the 12-week treatment period
 
For the United States:
 
The difference in the mean change from baseline in mean monthly migraine days across the 12-week treatment period between atogepant group and placebo in the Modified Intent-to-Treat (mITT) Population. Data after the discontinuation from double-blind treatment period will be excluded and assumed missing at random (MAR).
 
For the European Union
 
The difference in the mean change from baseline in mean monthly migraine days across the 12-week treatment period between atogepant group and placebo in the Off-treatment Hypothetical Estimand Population regardless of premature discontinuation of study drug. Data after starting a new migraine prophylaxis treatment use during the follow-up period will be excluded.

Objectives	Hypotheses	Estimands
Secondary Efficacy		

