## 2.2 Study Design Overview

This is a global, multicenter, randomized, double-blind, placebo-controlled, parallel-group study planned to be conducted at approximately 125 sites globally (North America, Europe, and Asia/Pacific).

[figure not shown]
Participation will begin with a 4-week screening/baseline period. Participants who complete the 4-week screening/baseline period and meet all entry criteria will be randomized to the double-blind treatment period of the study at Visit 2 (Randomization Visit). The double-blind treatment period will last 12 weeks, with a subsequent safety follow-up period of 4 additional weeks. Total duration of study participation for one participant is approximately 20 weeks.

There will be 8 scheduled clinic visits: Visit 1 (Screening/Baseline Visit), Visit 2 (Randomization Visit), Visit 3 (Week 2), Visit 4 (Week 4), Visit 5 (Week 6), Visit 6 (Week 8), Visit 7/ET (Week 12), and Visit 8 (Week 16/EOS/Follow-up). The Visit 8/EOS/follow-up period must be completed for all participants who take at least one dose of study intervention, except for participants rolling over into Study 3101-312-002 (long-term safety extension study). For these rollover participants Visit 8 is not required, because the final Follow-up Visit will be performed at the end of the long-term safety extension study. For participants who screen fail for the long-term safety extension study, the Follow-up Visit of Study 3101-304-002 must be completed.

Per study design (Protocol Sections 10.8.4 and 10.8.5), eDiary data will be collected for participants who early terminated from the double-blind treatment period during the 4 weeks between V7 (Early termination visit) and V8 (Follow-up Visit).

The schematic of the study is shown in [Figure 1](#).

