The secondary endpoints for headache days, acute medication use days, Performance of Daily Activities domain score of the AIM-D, and Physical Impairment domain score of the AIM-D will be analyzed in the same manner as that used to analyze the primary endpoint. For MSQ v2.1 Role Function Restrictive domain score and HIT-6 total score, the analysis will be performed similarly to the primary MMRM, with focus on the pairwise contrasts of atogepant dose group to placebo at Week 12. Some participants may have MSQ v2.1 or HIT-6 assessed at Visit 8, which will not be included in MMRM

models. Note that the stratification of number of migraine days during the screening/baseline period (4 to  $< 8$  and  $\geq 8$ ) will be included in the secondary efficacy analyses if baseline values other than monthly migraine days are included in the corresponding models.

The 50% responder, defined as a participant with the achievement of at least a 50% reduction from baseline in the 3-month average of monthly migraine days, will be assessed for each participant. A logistic regression model will be used to analyze the 50% responders across the 12-week treatment period. This model assumes a binary distribution for the response and uses a logit link. The analysis model will include treatment group, region, the stratification of number of classes of failed prior prophylactic treatments (2 and  $>2$ ), and baseline monthly migraine days. The treatment difference in terms of odds ratio between each atogepant dose group and placebo will be estimated and tested from this model.

For the analyses in the mITT population, the 50% responder will be derived using data collected from the double-blind period. For the analyses in Off-treatment Hypothetical Estimand population, the 50% responder will be derived using data collected from the double-blind period and follow-up period; data after participants started a new prophylaxis treatment during the follow-up period will be excluded.

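### Should the European estimand also remove, or test, double-blind data recorded after a participant starts a new preventive?

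*SAP*

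**What the plan says.** The European primary analysis (SAP 9.3.2) fits an MMRM to observed data from the double-blind and follow-up periods. Two intercurrent-event rules in SAP 8.0 and Table 4 matter here, and Table 5 repeats them for the European secondary endpoints.

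- **IE2.** A participant who starts a new preventive in either period "will have their data after starting the new migraine prophylaxis treatment during the follow-up period excluded from the analysis".
- **IE3.** A participant who stops study drug for any reason other than starting a new preventive keeps all off-treatment data in the analysis.

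Protocol 9.6.4 gives IE2 in a form that cannot be misread: such participants "will have their data during the safety follow-up period after starting the new migraine prophylaxis treatment excluded from the data analysis". Two places in the SAP are shorter. SAP 2.1 says "Data after starting a new migraine prophylaxis treatment use during the follow-up period will be excluded", and SAP 9.4.2, on the 50% responder endpoint, says "data after participants started a new prophylaxis treatment during the follow-up period will be excluded".

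Follow-up diaries are limited. The footnote to the Schedule of Activities (protocol 1.3) reads "For participants who terminate early from the double-blind treatment period only", and SAP 2.2 agrees: "eDiary data will be collected for participants who early terminated from the double-blind treatment period during the 4 weeks between V7" and V8. For the questionnaires, Visit 8 is when sites "administer PRO measures, including: EQ-5D-5L, HIT-6, and MSQ v2.1" (protocol 10.8.5), but SAP 9.4.2 adds: "Some participants may have MSQ v2.1 or HIT-6 assessed at Visit 8, which will not be included in MMRM" models.

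**The concern.** IE2 names double-blind starts as a trigger, yet the only data it can remove lie in follow-up. Three consequences look troubling.

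1. Someone who starts a preventive and stays on study drug contributes every later double-blind month to the European MMRM. That is treatment-policy handling inside an estimand labelled hypothetical, whose treatment condition (protocol 9.6.1) prohibits new preventives.
2. For HIT-6 and MSQ, both in the European testing sequence, the only follow-up value is Visit 8. It is outside the model, so IE2 appears to remove nothing.
3. The shorter wording in SAP 2.1 and 9.4.2 could be read as requiring the start itself to fall in follow-up. An early terminator who started a preventive before leaving would then keep follow-up data that protocol 9.6.4 excludes.

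Neither European check in SAP 9.3.3 isolates the effect. Copy-reference imputes missing values, and these values are observed. The US analysis, used as supplementary, excludes on discontinuation rather than on a start, so it keeps the same double-blind months. If placebo participants switched more, the estimate would be pulled toward no effect; if atogepant participants did, it would be inflated.

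**Working it through.** **The plan's own figure.** Inputs from protocol 9.2 and Table 9-2: 150 per arm, 15% dropout, difference 1.6 days, SD 3.5, two-sided 0.05.

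- Evaluable per arm: 150 × 0.85 = 127.5.
- SE = 3.5 × √(2/127.5) = 0.438; 1.6/0.438 = 3.65.
- Power from the noncentral t is 95.3%, against a stated 95%. It reproduces, and no stated figure depends on IE2.

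**What each wording does to diary data.**

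| Participant | Protocol 9.6.4; SAP 8.0, Tables 4 and 5 | SAP 2.1 and 9.4.2, read narrowly |
|---|---|---|
| Starts in double-blind, stays on drug to Week 12 | No follow-up diary; nothing removed | Same |
| Starts in double-blind, then terminates early | Follow-up data removed | Follow-up data kept |
| Terminates early, starts in follow-up | Later follow-up data removed | Same |

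The readings part only in the second row. There the trigger phrase in SAP 8.0 and Tables 4 and 5 names double-blind starts explicitly, which the narrow reading would make pointless.

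**How far IE2 can reach.** Early terminators at the planned dropout: 0.15 × 300 = 45. One 28-day follow-up can fall in two analysis months. With a last dose on Day 42, follow-up runs over Days 43–70: 14 days in Weeks 5–8 and 14 in Weeks 9–12, which meets the 14-diary-day rule in SAP Appendix B. With complete diaries this happens for last doses on Days 14–27 or 42–55. The ceiling is 45 × 2 = 90 of 300 × 3 = 900 participant-months (10%), reached only if every early terminator fits that pattern and has started a preventive.

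**What the retained double-blind data could do.** The documents give no switching rate and no benefit. Assumed: a net 2–10% of one arm (3–15 of 150) starts a preventive while on study drug, from Week 9 or Week 5, so that 1/3 to 2/3 of the 12 weeks is affected.

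- *Primary*, assumed benefit 1–2 days per month. Shift = share × benefit × fraction: 0.02 × 1 × 1/3 = 0.007 to 0.10 × 2 × 2/3 = 0.133 days, or 0.4% to 8.3% of 1.6. If toward no effect, the far end leaves 1.467 days and 91.5% power.
- *HIT-6 at Week 12* (planned 3.9, SD 7.6), assumed benefit 1–3.9 points. Shift = share × benefit: 0.02 × 1 = 0.02 to 0.10 × 3.9 = 0.39. Power goes from 98.3% to 95.7% at the far end.
- *MSQ at Week 12* (planned 10.9, SD 22.8), assumed benefit 2.8–10.9 points: 0.02 × 2.8 = 0.06 to 0.10 × 10.9 = 1.09. Power goes from 96.7% to 92.8% at the far end.

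The far ends stack generous assumptions. They give the new preventive the whole planned atogepant effect on HIT-6 and MSQ, and more than it on migraine days (2 against 1.6), in people who had already failed 2 to 4 classes. Equal switching with equal benefit in both arms gives no shift.

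**The case for a change.** The best case for a change is that it is cheap and the gap is real. Nothing in the plan removes double-blind data after a start. Starting a preventive is prohibited, but it is not among the conditions that require withdrawal in protocol 7.1, and protocol 6.5.3 asks only that the sponsor be told. The medication and deviation summaries (SAP 7.3 and 7.4) give an idea of frequency, not of effect on the estimate. Start dates are already recorded (protocol 6.5), so a filtered analysis would be possible.

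Those facts stand, but they do not amount to a defect.

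- **The rule is stated and the analysis follows it.** Protocol 9.6.4 limits the exclusion to follow-up data. The estimand's name can fairly be read as applying the hypothetical strategy to off-treatment data.
- **Naming double-blind starts has a purpose.** IE3 treats starting a preventive as a reason for stopping study drug. Under protocol 7.1 that ends participation, and the participant enters follow-up, where IE2 acts. The remaining group breaks the prohibition and also stays on drug.
- **The extra analysis would answer a different question.** Dropping double-blind data after a start changes the intercurrent-event strategy, so by the SAP's own usage it would be supplementary, not a sensitivity analysis. It would treat a start, which may signal treatment failure, as missing at random. It would need a debatable rule for responders and a definition of a new preventive, since protocol 6.5.3 bars the listed drugs whatever the indication.
- **The loose wording has a fuller source.** For the primary endpoint, the planned US analysis uses none of the follow-up data on which the two readings differ.

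**Conclusion.** No change is needed. Keeping double-blind data after a start is a defensible treatment-policy choice, set out in protocol 9.6.4 and carried through SAP 8.0 and Tables 4 and 5. For HIT-6 and MSQ, IE2 is a repeated table entry with nothing to act on, which does no harm. The shorter sentences in SAP 2.1 and 9.4.2 are a slip in wording that an analyst would settle from the full rule.

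The true effect is unknown because no switching rate is given. Under the assumed ranges it is at most 0.13 days on the primary endpoint, 0.39 points on HIT-6 and 1.09 points on MSQ. Even if all of it ran toward no effect, power would stay at 91.5%, 95.7% and 92.8% respectively. The conclusion rests on net switching in one arm while on study drug not exceeding about 10%. If the medication and deviation tables show much more than that, or a marked imbalance between arms, a supplementary look at those participants could be added when the trial is reported.

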### Primary analysis in support of the submission in the US

The primary endpoint will be analyzed using a mixed model for repeated measures (MMRM) on the mITT population. The response variable is the change from baseline to each postbaseline month in monthly migraine days. The model will include treatment group, visit (derived as Weeks 1 - 4, Weeks 5 - 8, and Weeks 9 - 12), region, number of classes of failed prior prophylactic treatments (2 and >2), and treatment group by visit interaction as categorical fixed effects. It will also include the baseline monthly migraine days and baseline-by-visit interaction as covariates. Note that baseline monthly migraine is included in the primary model, therefore the stratification of number of migraine days during the screening/baseline period (4 to < 8 and  $\geq$  8) will be excluded in the primary model. The analysis will be performed based on evaluable postbaseline data using only the observed cases without missing data imputation. For submission in the US, only data collected during the double-blind period will be included in the analysis.

Restricted maximum likelihood method will be used. The within-patient correlation will be modeled using the unstructured covariance matrix. If the model does not converge, then the Toeplitz covariance structure will be used. If the model with the Toeplitz covariance structure does not converge, then the compound symmetry covariance structure will be used. The Kenward-Roger approximation will be used to estimate denominator degrees of freedom. Contrast will be constructed to obtain the average treatment effects across the 12-week treatment period to compare atogepant treatment group versus the placebo group. Treatment effect and treatment comparison will be estimated by the LS Means and their difference in LS Means, along with their SE and 95% confidence interval, and the p-value corresponding to the between-treatment group difference.

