9.4.1.2. Primary Analyses

The primary efficacy analysis is the change from baseline in mean monthly migraine days across the 12-week treatment period.

The primary comparison between treatment groups will be done by a MMRM of the change from baseline. The statistical model will include treatment group, visit, region, number of classes of failed prior prophylactic treatments, and treatment group by visit interaction as categorical fixed effects. It will also include the baseline value and baseline-by-visit interaction as covariates. An unstructured covariance matrix will be used to model the covariance of within-participant repeated measurements. Note that baseline monthly migraine is included in the primary model, therefore the stratification of number of migraine days during the screening/baseline period (4 to < 8 and ≥ 8) will be excluded in the primary model. On the other hand, this stratification will be included in the secondary and exploratory analyses if baseline values other than monthly migraine days are included in the corresponding models. The Kenward-Roger approximation ([Kenward and Roger 1997](#)) will be used to estimate the denominator degrees of freedom. The analysis will be performed based on all postbaseline values using only the observed cases without imputation of missing values. Pairwise contrasts in the MMRM model will be used to make the pairwise comparisons of each atogepant dose to placebo. Only data collected during the double-blind period will be included in the analysis. Participants are always analyzed based on the treatment group assigned by randomization.

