**Figure 1. Study Schematic**

### 2.3 Treatment Assignment and Blinding

Approximately 300 participants will be randomized to one of 2 treatment arms (placebo, and atogepant 60 mg QD) in a 1:1 ratio as follows:

- Placebo (n = 150)
- Atogepant 60 mg QD (n = 150)

Randomization will be stratified based on region (North America, Europe, and Asia/Pacific), number of migraine days during the screening/baseline period (4 to < 8 and  $\geq 8$ ) and number of classes of failed prior prophylactic treatments (2 and > 2). Block randomization will be applied with a block size of 4 (2 treatment arms  $\times$  2). Though the study was planned to include sites in Asia/Pacific, no participants were enrolled from this region.

A randomization cap of 20% will be instituted to ensure that the planned randomized participants include no more than 20% of participants with 4 to <8 migraine days at baseline. Approximately 50% of randomized participants will have failed > 2 classes of prior prophylactic treatments.

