## **2.4 Sample Size Determination**

A sample size of 150 randomized participants per treatment group will provide a 97% and 95% power to detect the treatment difference of -1.7 or -1.6 between atogepant and placebo for the primary efficacy endpoint for the United States or the EU, respectively. This sample size was selected to provide sufficient power for each of the secondary endpoints in [Table 1](#) for the United States and in [Table 2](#) for the EU.

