## **13.0 Overall Type-I Error Control**

A fixed-sequence procedure will be used for multiple comparisons to control the family-wise Type I error rate at a 0.05 level. Once the primary endpoint for atogepant dose is significant at 0.05 (2-sided), the secondary endpoints will be tested. The testing sequence is specified for the US and EU in [Table 6](#) and [Table 7](#).

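### The covariance fallback in SAP 9.3.2 assumes equal variance at every visit; if it is ever used, the confirmatory Week 12 tests of MSQ and HIT-6 may miss the 5% level in either direction

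*SAP*

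**What the plan says.** Protocol 9.4.1.2 names one covariance structure for the primary model: "An unstructured covariance matrix will be used to model the covariance of within-participant repeated measurements". It specifies Kenward-Roger degrees of freedom.

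SAP 9.3.2 keeps the unstructured matrix as first choice and adds an order of retreat: "If the model does not converge, then the Toeplitz covariance structure will be used". If Toeplitz also fails, "then the compound symmetry covariance structure will be used". Kenward-Roger applies throughout. No heterogeneous-variance form and no empirical standard error is named. The primary contrast is the average over the three months.

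SAP 9.4.2 analyses MSQ Role Function-Restrictive and HIT-6 similarly to the primary MMRM, "with focus on the pairwise contrasts of atogepant dose group to placebo at Week 12". Visit 8 is left out, so under the schedule of activities these models have three post-baseline visits: Weeks 4, 8 and 12.

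SAP 13.0 places these tests in the confirmatory family: "A fixed-sequence procedure will be used for multiple comparisons to control the family-wise Type I error rate at a 0.05 level". In SAP Tables 6 and 7, MSQ at Week 12 is US S4 and EU S5, and HIT-6 at Week 12 is EU S4.

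**The concern.** Toeplitz and compound symmetry in their standard forms carry a single variance parameter. A contrast at one visit then takes its standard error from a variance pooled over all visits. If the spread of change scores widens with time, the Week 12 standard error is too small and the test rejects too often. If the spread narrows, the test is conservative. Kenward-Roger adjusts for small samples within the chosen structure; it does not repair a wrong structure.

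At stake is the level of three confirmatory tests. In a fixed sequence each step is tested at the full 0.05, so a step that runs above 0.05 puts the family-wise rate above 0.05 whenever the earlier nulls are false and that step's null is true. US S4 also gates the two AIM-D endpoints, and EU S4 gates MSQ. The sensitivity analyses in SAP 9.3.3 cover only the primary endpoint, so none would show the problem for MSQ or HIT-6.

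**Working it through.** **Inputs from the documents.** Two-sided 0.05 (SAP 13.0); 150 per arm, 1:1 (SAP 2.3, 2.4); 15% dropout for endpoints other than AIM-D, giving 150 × 0.85 = 127.5 evaluable per arm (SAP 2.4); differences and SDs from SAP Tables 1 and 2.

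**Input not in the documents.** The SDs of MSQ and HIT-6 change at Weeks 4 and 8. Only Week 12 SDs are given (22.6 and 22.8 for MSQ, 7.6 for HIT-6). I assume a Week 12/Week 4 SD ratio g, with Week 8 midway, and vary g from 0.8 to 1.5.

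**Step 1: reproduce the plan's power.** Power = Φ(|δ|/SE − 1.96), with SE = SD × √(2/127.5).
- US primary: SE = 3.5 × 0.1252 = 0.438; 1.7/0.438 = 3.88; power 97.2% (stated 97%).
- EU primary: 1.6/0.438 = 3.65; 95.5% (stated 95%).
- US MSQ: 10.8/2.83 = 3.82; 96.8% (stated 96%).
- EU MSQ: 10.9/2.86 = 3.82; 96.8% (stated 96%).
- HIT-6: 3.9/0.952 = 4.10; 98.4% (stated 98%).

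The planning figures reproduce to within one point. The documents state no error rate under the fallback.

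**Step 2: closed form, complete data.** With one common variance, the Week 12 standard error uses the pooled SD, √[(s4² + s8² + s12²)/3]. Let r = s12 / pooled SD. The true two-sided error is 2 × [1 − Φ(1.96/r)].

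Example, g = 1.25 (SDs at 80%/90%/100% of the Week 12 value): pooled variance relative to Week 4 = (1 + 1.2656 + 1.5625)/3 = 1.276; r = 1.25/1.1296 = 1.107; 1.96/1.107 = 1.771; error = 7.7%.

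**Step 3: simulation under the null.** REML fits with the SAP's fixed effects, 150 per arm, three visits, about 15% monotone MAR dropout, assumed correlations 0.65/0.55/0.70, and model-based standard errors with a t test in place of Kenward-Roger. There were 8,000 replicates for g = 1.0 to 1.3 (Monte Carlo SE about 0.3 points at 8%) and 3,000 for g = 0.8 and 1.5.

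Week 12 type I error:

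| g | Closed form | Toeplitz | Compound symmetry | Unstructured |
|---|---|---|---|---|
| 0.8 | 2.7% | 2.8% | 2.9% | 5.0% |
| 0.9 | 3.8% | – | – | – |
| 1.0 | 5.0% | 4.9% | 5.0% | 5.1% |
| 1.1 | 6.1% | 6.0% | 6.2% | 5.0% |
| 1.2 | 7.2% | 7.3% | 7.5% | 4.9% |
| 1.3 | 8.1% | 8.0% | 8.3% | 4.8% |
| 1.5 | 9.8% | 9.6% | 9.8% | 4.9% |

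The closed form reaches exactly 8% at g ≈ 1.29. A separate simulation (correlation 0.6, 2,500 replicates, with and without about 13% dropout) gave 8.0-8.2% at g = 1.25, against 5.0-5.2% unstructured. A smaller 3,000-replicate run of the Step 3 model at g = 1.3 gave 8.9% and 9.1%, with unstructured at 5.6%; its Monte Carlo SE is about 0.5 points.

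**Step 4: the 12-week average.** Its variance is one ninth of the sum of all nine covariance elements. With complete data, compound symmetry replaces the variances by their mean and the covariances by theirs, which leaves that sum unchanged. Toeplitz comes close to the same result. In Step 3 the average contrast ran at 4.9-5.4% under either fallback for g = 1.0 to 1.3, and at about 5.6% for g = 1.5.

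**The case against.** The strongest objection is that the trigger will hardly ever occur. An unstructured 3 × 3 matrix has six parameters, and about 255 to 300 participants inform it. A trial fit of the unstructured REML model by Fisher scoring, with about 14% dropout, failed in 0 of 1,000 datasets at 150 per arm and 0 of 1,000 at 30 per arm. That solver is not SAS, but the direction is clear. If the chance of fallback were 1% (an assumption), 8% against 5% would add 0.01 × 3 = 0.03 points to the overall Week 12 error; at 5% it would add 0.15 points. This stands, and it sets the priority.

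Second, the rise in SD is assumed. Nothing in either document shows that the spread of MSQ or HIT-6 change grows over visits; it could be constant or fall. This also stands, so the range must be shown on both sides of 5%.

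Third, a reader might infer that the SAP contradicts the protocol because the protocol names only the unstructured matrix. The documents do not support that as a defect. Protocol 9.4 describes itself as a summary and leaves analysis definitions to the SAP, and fixing the order of retreat in advance is good practice. The weakness lies in which structures were chosen.

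What remains is that a pre-specified fallback should hold its level when it is used, and this one does so reliably only if the variance does not grow.

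**Conclusion.** The point holds conditionally and is minor. Two things must both happen for the Week 12 tests of MSQ (US S4, EU S5) and HIT-6 (EU S4) to exceed 5%: the unstructured fit fails, and the SD of change rises over visits. With growth of about 25-30% from Week 4 to Week 12, the level is then about 8%. Over assumed ratios of 0.8 to 1.5 it runs from about 3% to about 10%, and it is 5% if the SD is constant. The figures also rest on reading the SAP's Toeplitz as the homogeneous form, since it does not say otherwise.

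A reader might infer that the plan's family-wise control fails, or that the primary result is at risk. Neither follows. With the planned unstructured matrix the Week 12 contrasts stay near 5%. The primary and the other 12-week-average contrasts are essentially unaffected even under the fallback. The fair statement is that control at 0.05 is not assured for the Week 12 steps if the fallback is used.

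**What to change.** Optional and low priority. Replace the fallback sentences in SAP 9.3.2, which SAP 9.4.2 then inherits, with this order:

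1. If the unstructured model does not converge, refit the same matrix in another parameterisation (for example, Cholesky) or with new starting values.
2. If that fails, use heterogeneous Toeplitz.
3. If that fails, use heterogeneous compound symmetry.

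Keep Kenward-Roger throughout. The wording should be settled before unblinding, so that no covariance choice is made with treatment codes known.

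The cost is a sentence or two and standard software options. With three visits, each fallback carries two more covariance parameters than its homogeneous counterpart: five against three for Toeplitz, four against two for compound symmetry. A richer fallback is slightly more likely to fail in its turn. Nothing changes if the unstructured fit converges, and endpoints, sample size and testing order stay as they are.

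A mandatory sandwich standard error with between-within degrees of freedom is not needed. Visit-specific variances already remove the problem, and the sandwich route would displace the Kenward-Roger method that the protocol specifies.
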